Comparing the Effects of Upper and Lower Body Resistance Training on Pain Sensitivity

NCT05985382

7/28/2023

STUDY PROTOCOL

This study was a crossover trial of healthy participants. Participants completed a lower body resistance exercise and an upper body resistance exercise in a counterbalanced order across two sessions. Immediately before and after each intervention, participants underwent heat pain threshold and pressure pain threshold.

During the first session, participants underwent familiarization of the heat and pressure pain threshold followed by a 5 repetition maximum test for the upper body and lower body resistance exercise.

In the second and third session, participants underwent either a lower or upper body exercise in a counterbalanced order.

Lower body exercise was a bilateral leg extension conducted at 75% of the estimated 1 repetition maximum. 3 sets of 10 repetitions were performed.

Upper body exercise was a bilateral overhead shoulder press conducted at 75% of the estimated 1 repetition maximum. 3 sets of 10 repetitions were performed.

STATISTICAL ANALYSIS

To examine the immediate changes in heat and pressure pain threshold by condition, separate repeated measures ANOVAs were conducted. Simple effects decomposition with Bonferroni correction were completed. Our a priori alpha level is <0.05.

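### Bonferroni is valid for the simple effects, but if the family holds two or more tests Holm's step-down gives the same familywise control and never rejects less

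*Combined protocol and SAP*

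**What the plan says.** The Study Protocol section describes a within-person comparison of two exercises: "Participants completed a lower body resistance exercise and an upper body resistance exercise in a counterbalanced order across two sessions". Both pain measures are taken on each side of each exercise: "Immediately before and after each intervention, participants underwent heat pain threshold and pressure pain threshold". Each measure therefore has a layout of two conditions by two times.

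Under Statistical Analysis, heat and pressure pain threshold are analysed apart ("separate repeated measures ANOVAs were conducted"). The follow-up is "Simple effects decomposition with Bonferroni correction were completed", and the significance level is given as "Our a priori alpha level is <0.05".

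The section does not list the simple effects, say how many share one correction, or say whether a family covers one pain measure or both. It gives no sample size, power or effect size, and mentions neither a step-down procedure nor confidence intervals.

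**The concern.** With no variant named, the natural reading is ordinary single-step Bonferroni, which compares every p-value in a family of m with 0.05/m. Holm compares the smallest with 0.05/m, the next with 0.05/(m-1), and so on up to 0.05, stopping at the first failure. Its first threshold equals Bonferroni's and the later ones are larger, so it cannot lose a rejection. Its familywise guarantee needs no assumption about dependence, which matters here because all the tests come from the same participants.

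What is at stake is the second finding. Take m = 2, with p = 0.01 for one exercise and p = 0.04 for the other. Bonferroni compares both with 0.025 and declares only the first. Holm passes the first at 0.025, then compares the second with 0.05 and declares both. When both changes are real, Bonferroni will more often report only one of them.

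**Working it through.** **Inputs from the documents.** Alpha 0.05; Bonferroni for the simple effects; two conditions, two times, and a separate ANOVA for each measure. There is no stated power or adjusted alpha to reproduce.

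**Assumed inputs.** Two-sided tests; m = 2 (pre-to-post change within each exercise, one measure); 80% power for each effect at unadjusted 0.05; both effects real unless stated.

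**Thresholds for m = 2.** Bonferroni 0.025 and 0.025; Holm 0.025 and 0.05.

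**Direct calculation, independent normal test statistics.**
- The mean of the test statistic that gives 80% power is 1.960 + 0.842 = 2.802.
- Power of one test at 0.025: P = Φ(2.802 - 2.241) = 0.712.
- Chance that a p-value falls between 0.025 and 0.05: 0.800 - 0.712 = 0.088.

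| Quantity | Bonferroni | Holm |
|---|---|---|
| Power per effect | 0.712 | 0.712 + 0.088 × 0.712 = 0.775 |
| Power for both | 0.712² = 0.507 | 0.800² - 0.088² = 0.632 |
| At least one rejection | 1 - 0.288² = 0.917 | 0.917 |
| One real, one null: power for the real effect | 0.712 | 0.712 + 0.088 × 0.025 = 0.714 |
| One real, one null: false rejection of the null effect | 0.025 | 0.025 + 0.712 × 0.025 = 0.043 |

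**Simulation, normal statistics** (400,000 replicates per setting, correlation 0 or 0.5). With both effects real, power per effect is 71% under Bonferroni and 77-78% under Holm; power for both is 51-57% and 63-68%. The chance of at least one rejection is the same under both methods (0.917 at correlation 0, 0.853 at 0.5). Holm kept every Bonferroni rejection in every replicate. The largest familywise error for either method was 0.0498.

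**Simulation, paired t tests** (60,000 trials per setting; n = 20, 30 or 40; correlation 0 to 0.6 between the change scores). Standardised effects of 0.660, 0.529 and 0.454 give 80% unadjusted power at the three sample sizes. Power per effect is about 70-71% against 75-77%, and power for both about 49-58% against 63-69%. At n = 30 and correlation 0.3 the figures are 0.702 and 0.528 for Bonferroni, and 0.764 and 0.653 for Holm.

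**Chance that exactly one of two equal, real effects is significant** (n = 30, correlation 0.3). This is twice the gap between power per effect and power for both:
- Bonferroni: 2 × (0.702 - 0.528) = 0.35.
- Holm: 2 × (0.764 - 0.653) = 0.22.

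Holm makes the split result less frequent but does not remove it.

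**The case against.** The strongest case is that Bonferroni is a valid procedure, chosen in advance, so the remark is a preference that applies to any plan naming it. The first half stands: nothing in the plan is wrong or contradictory here. The second half does not dispose of the point, because a procedure with the same guarantee that never rejects less is a concrete improvement.

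Other objections narrow the point, and they stand:
- **The gain may be zero.** The family is undefined. If the correction is applied within each pre-to-post contrast on its own, m = 1 and the two methods coincide.
- **The gain is conditional.** Holm adds a rejection only after one test has already passed 0.05/m. With one real effect and m = 2 it adds about 0.2 percentage points.
- **A family of four should not be used to size the gain.** A reader might infer a much larger loss from four real effects. Within one ANOVA, the four simple effects would include a comparison of the exercises before either session's exercise, which is expected to be null, and the four contrasts are linearly dependent. Four real pre-to-post changes would need one family spanning heat and pressure, and the separate ANOVAs do not suggest that.
- **There is a price.** Holm has no equally simple simultaneous intervals. When one effect is null and the other real, the chance of falsely rejecting the null one rises from 2.5% to about 4.3%, still inside the 5% familywise limit.
- **The comparison of exercises lies elsewhere.** A reader might infer that Bonferroni endangers the trial's main comparison by showing one exercise as working and the other not. Whether the exercises differ is tested by the condition-by-time interaction, not by comparing the significance of two simple effects, and Holm does not repair that inference.
- **Timing.** The section is in the past tense. Adopting a procedure that can only reject more, once p-values are known, is a post hoc change.

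**Conclusion.** The point holds as an optional efficiency gain. For any family of two or more simple effects, Holm gives the same 5% familywise control under any dependence and rejects at least as much.

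With m = 2, both effects real and 80% unadjusted power, the two simulations together put power per effect at about 70-71% under Bonferroni and 75-78% under Holm, and power for both at about 49-58% and 63-69%. These figures rest on assumed inputs; the loss in this trial cannot be calculated, because family size, sample size, effect sizes and correlation are all unstated.

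A reader might go further and infer that the plan gives power away for nothing. The documents do not support that: it is not established that the family exceeds one test or that more than one effect is real, and Bonferroni keeps simple matching intervals. Nor do they support calling the choice an error.

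**What to change.** If results have not been seen, replace the simple-effects sentence with: 'Simple effects decomposition with Holm step-down correction at a familywise 0.05'. Report Holm-adjusted p-values, and keep Bonferroni intervals if intervals are reported. State that any claim of a difference between the exercises rests on the condition-by-time interaction.

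If results have already been seen, keep Bonferroni as the stated analysis and report the Holm-adjusted p-values beside it, labelled post hoc.

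In either case, say which simple effects form the family; without that neither correction can be reproduced.

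The cost is a short text change and a re-ranking of the p-values. No new data, model or alpha is needed. The downside is that the Bonferroni intervals will not always agree with Holm's decisions: an effect declared at a later Holm step can have a Bonferroni interval that includes zero, and the report should say so.
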